The current practice of maintaining a high UO in otherwise well patients by liberal fluid infusions can be therefore be questioned. More importantly, a series of recent randomised clinical trials demonstrate that liberal fluid therapy approximately doubles postoperative complication rates as compared to a more restricted fluid regime, confirming findings in animal studies of numerous detrimental effects of perioperative fluid overloading. Three clinical trials demonstrate a relative reduction of 46%, 45% and 84% of overall postoperative morbidity with restricted fluid therapy, clearly identifying fluid overloading as a major, iatrogenic and preventable cause of complications in contemporary surgical care. The main obstacle to fluid restriction in practice is maintaining the traditional high UO target. This study therefore aims to demonstrate that a lower UO target is not associated with renal impairment, confirming previous observational studies.

Aims

This study tests the hypothesis that a urine output target lower than the traditional 0.5 ml/kg/h (0.2 ml/kg/h) does not cause harm to the kidneys. Harm is defined in the widest sense of the word in order to detect any degree of harm. It is therefore evaluated by several highly sensitive methodologies beyond the routinely used serum concentrations of creatinine and urea. These methods include frequent sampling for novel, validated biomarkers of renal stress (neutrophil gelatinase-associated lipocalin (NGAL) and Cystatin C) in combination with renal clearance studies to directly measure renal plasma flow (para-aminohippurate (PAH) clearance) and glomerular filtration rates (Sinistrin clearance).

Importance

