Baseline measures of effective renal plasma flow (ERPF), glomerular filtration rate (GFR), AKI biomarkers, plasma creatinine and renoregulatory hormones are obtained prior to surgery. Participants are randomised to the Low (0.2 ml/kg/h) or High (0.5 ml/kg/h) groups on induction of general anaesthesia. Randomisation is stratified by baseline renal function. Surgical techniques are per surgeon preference. Perioperative care is standardised according to the North Shore Hospital (NSH) enhanced-recovery after surgery (ERAS) protocol to minimise variation in ancillary care. This includes routine usage of epidural analgesia, routine urinary catheterisation until morning of postoperative day (POD) 2 and a standardised perioperative fluid protocol (see Table 1). During surgery and the next 48 hours, UO is monitored hourly. In both groups, an hourly UO <0.5 ml/kg/h prompts immediate anaesthetic or surgical team review to rule out evidence of potential hypoperfusion of any aetiology (see Figure 1). If this is not present, patients in the High group will receive 500-ml fluid boluses (Plasma-Lyte 148) until UO exceeds 0.5 ml/kg/h. In the Low group, fluid boluses will be only given if UO falls below 0.2 ml/kg/h.

The main endpoint is the urinary NGAL on POD 1. Neutrophil gelatinase-associated lipoprotein, the best-validated and most sensitive biomarker of AKI, will be followed 12-hourly during 48 hours. In addition, plasma cystatin C and creatinine concentrations, urinary electrolytes and osmolality will be measured several times per day, and the ERPF and GFR measurements will be repeated on POD 1. Renoregulatory hormones will also be followed. The study nephrologist will acutely assess any participant with a persistently

Table 2. Exclusion criteria
Preexisting moderate or severe chronic kidney disease (eGFR <60 ml/min/1.73 m ²)
Pre-existing kidney damage regardless of eGFR (single functional kidney, renal transplant, significant proteinuria)
History of previous AKI due to any cause (AKI Network Stage 2)
Need for ongoing angiotensin-converting enzyme inhibitors, angiotensin receptor blockers or non-steroidal anti-inflammatory drugs (NSAIDs)
Nephrotoxic substance administration (including systemic radiocontrast dyes, aminoglycosides, glycopeptides and NSAIDs other than aspirin) within 48 h prior to surgery
Pre-existing hepatic failure (Child-Pugh Score >6)
ASA class IV
Morbid obesity (BMI>35)
Intraoperative ureteric injury

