Intraoperative haemorrhage >50% of blood volume
Pregnant or lactating females

low UO despite a total bolus volume of 2 l or a plasma creatinine increase by ≥ 2 -fold compared to baseline at any point. Clinical outcomes will also be recorded.

Participants

Forty men and women aged between 18 and 85 years of age, able to give informed consent, undergoing elective segmental colectomy for benign or malignant disease, by laparotomy or laparoscopy will be studied. Participants will be recruited among patients undergoing bowel surgery at North Shore Hospital. Exclusion criteria are listed in Table 2.

Step-by-step protocol

Recruitment: With the permission of the potential participant, a research fellow or research nurse gives a brief oral and written (Participant's Information Sheet) information about the study in outpatients clinic. The research fellow or research nurse telephones the potential participant 3-7 days later to further discuss the study and seek oral consent. If consent is given, patient attends a separate research visit approximately one week prior to surgery, where written consent is obtained prior to any test procedures.

Preoperative research outpatients visit: Baseline renal function measures will be performed on a dedicated research visit to outpatients clinic approximately one week prior to surgery. Patients present at 9 am overnight fasted. Two IV cannulas are placed. A 3-hour intravenous infusions of sinistrin and PAH is given with the participant resting in a reclining armchair (see Clearance Studies protocol). One urine sample and three blood samples will be taken on this occasion for baseline measures of urinary NGAL, plasma creatinine, cystatin C, electrolytes, osmolality, C-reactive protein (CRP), glucose, and renoregulatory hormones. Plasma concentrations of sinistrin and PAH are determined for calculation of ERPF and GFR. Body composition will be estimated using bioimpedance analysis (BIA).

Randomisation: Participants are randomised (allocation concealment by off-site computer randomisation, The University of Auckland) to the Low or the High group on induction of general anaesthesia.

Study period: The data collection period starts before surgery and ends on POD 30.

Study intervention: The only difference between the two study groups is the response to urine output below 0.5 ml/kg/min from start of anaesthesia until 8am on POD 1 (see Figure 1).

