Urinary output is followed hourly. All anaesthetic and surgical teams providing care for participants will be educated face-to-face about the details of the fluid protocols. A research fellow will monitor compliance with protocols around the clock in person and over the phone.

Participants with epidural-related hypotension will follow the standard ERAS protocol (a combination of fluid boluses and reduced epidural infusion rates).

Participants with complications remain in the study. As per the study fluid algorithms (Figure 1), the UO target in the Low group will switch from 0.2 to 0.5 ml/kg/h if there are any signs of hypoperfusion.

At the routine 30-day outpatients clinic followup, a final urine and plasma sample will be collected.

Nephrologist review triggers: The on-site study nephrologist [name] (or a named colleague in his absence) will urgently (within 12 hours) review any participant with an absent UO response to a 2L fluid bolus (see Figure 2), or with AKI Network (AKIN) stage 2 AKI per creatinine criteria (persistent elevations of plasma creatinine $\geq 100\%$ above baseline despite adequate fluid resuscitation) within 30 days, and institute adequate therapy.

Independent Monitoring Committee: Two independent senior consultant nephrologists ([name] at Auckland City Hospital and [name] at Middlemore Hospital) make up an independent Monitoring Committee, which will review individual clinical outcomes as well as postoperative changes in plasma creatinine in all participants after completion of four and 20 participants.

Study halt triggers: In addition, the study will be halted pending urgent review by the independent Monitoring Committee if the following occurs: Two or more participants in the intervention arm develop AKI Network (AKIN) stage 3 AKI per creatinine criteria (persistent elevations of plasma creatinine $\geq 200\%$ above baseline despite adequate fluid resuscitation) within seven days after surgery and in the absence of a clear-cut alternative cause (such as major systemic complication of surgery).

Table 3. Secondary endpoints
Urinary excretion of NGAL 0800 POD1 - 0800 POD 2 and total excretion during intervention period
Urinary concentrations of NGAL and creatinine and osmolality during and after surgery
Plasma concentrations of cystatin C, creatinine, ADH, aldosterone, renin and angiotensin II and osmolality during and after surgery
ERPF and GFR before and 1 day after surgery

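### The creatinine trigger for nephrologist review is given in two versions: any doubling, or only a persistent doubling despite fluid resuscitation

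*Protocol*

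**What the plan says.** The rule appears in two places, both current text.

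- **Study design.** The sentence begins "The study nephrologist will acutely assess any participant with a persistently", is interrupted by Table 2, and resumes "low UO despite a total bolus volume of 2 l or a plasma creatinine increase". Its creatinine part reads in full "a plasma creatinine increase by ≥ 2 -fold compared to baseline at any point".
- **Step-by-step protocol, Nephrologist review triggers.** The on-site study nephrologist, or a named colleague, "will urgently (within 12 hours) review any participant with an absent UO response to a 2L fluid bolus". The alternative trigger is AKI Network "stage 2 AKI per creatinine criteria (persistent elevations of plasma creatinine" at least 100% "above baseline despite adequate fluid resuscitation) within 30 days, and institute adequate therapy".

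The neighbouring Study halt triggers paragraph uses the same form of words one stage higher: "stage 3 AKI per creatinine criteria (persistent elevations of plasma creatinine" at least 200% above baseline, within seven days, in two or more intervention-arm participants and without a clear alternative cause.

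**The concern.** One safety action, taken by one reviewer at one threshold, has two different entry conditions. Staff who consult the paragraph headed as the trigger list would have no instruction there to call the nephrologist for a first or fluid-responsive doubling, although the Study design section requires acute assessment of it.

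The trial asks whether a lower urine output target harms the kidney, so this rule protects the participants in whom the hypothesis would be failing. The added fluid condition may also bear unequally on the arms. Without signs of hypoperfusion, High-group participants receive boluses when urine output is below 0.5 ml/kg/h, and Low-group participants only when it is below 0.2 ml/kg/h. During the intervention period, a Low-group participant at 0.3 ml/kg/h with a doubled creatinine may have had no bolus for urine output. Read literally, the narrower trigger may then not be met until fluid is given.

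**Working it through.** No design figure depends on this rule, so the check is a comparison of the two texts.

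**Step 1: is the threshold the same?** A 2-fold value is 2.0 × baseline. The increase over baseline is (2.0 − 1.0) × 100% = 100%. The thresholds agree.

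**Step 2: what does the Study design sentence attach to creatinine?** The sentence has two limbs joined by *or*. The adverb for persistence and the 2-litre bolus condition both sit in the urine output limb. The creatinine limb has only the threshold and an unrestricted time reference.

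**Step 3: what does the trigger paragraph add?**

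| Element | Study design | Nephrologist review triggers |
|---|---|---|
| Reviewer | Study nephrologist | Study nephrologist or named colleague |
| Threshold | At least 2.0 × baseline | At least 100% above baseline (the same) |
| Persistence required | No | Yes |
| Adequate fluids required first | No | Yes |
| Window | Any point | Within 30 days |
| Response | Acute assessment | Urgent review within 12 hours |

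The windows hardly differ in practice, because data collection ends on postoperative day 30. The substantive differences are the persistence and fluid conditions.

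**Step 4: which participants are classified differently?** Given a doubled creatinine:

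| | Adequately fluid-resuscitated | Not yet |
|---|---|---|
| Persistent | Both trigger | Study design only |
| Not persistent, or not yet shown to be | Study design only | Study design only |

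The statements agree only when both conditions are met. The table lists situations, not patients. They are not equally likely, and the document gives no event rate from which to estimate their frequency or the length of any delay.

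**Step 5: can the added conditions be applied?** The visible text defines neither. Under Endpoints, plasma is sampled at regular intervals to 72 hours after surgery and then once on day 30. A doubling first seen in the last of the early samples, or on day 30, has no scheduled repeat soon enough to show persistence within the window. The detailed sampling appendix is not among the visible pages, so this rests on the Endpoints section alone.

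**The case against.** The strongest reply is that the two statements are compatible. The trigger paragraph does not say that only its cases are reviewed, and a site following the whole protocol would assess every doubling and apply the 12-hour limit to the confirmed subset. The Study design sentence could also be an overview of the later detail. It is loose on urine output too, where a persistently low output in one place becomes an absent response in the other, and its open time reference may simply stand for the 30-day window.

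Practical safeguards narrow the gap. Creatinine is measured several times a day early on, a research fellow monitors compliance around the clock, urine output below 0.5 ml/kg/h prompts team review in both groups, and the Monitoring Committee looks at creatinine changes. Which section staff would consult is conjecture. The stated aim of detecting any degree of harm also leads into a list of outcome measurements, not a rule for calling a nephrologist.

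Much of this stands as a limit on importance. It does not remove the discrepancy. Joint compliance is possible, but no visible text says it is intended. A summary may leave out detail, but an unrestricted time reference fits poorly with a persistence requirement. The safeguards do not fully cover the gap: hourly urine monitoring lasts for surgery and the next 48 hours, the catheter comes out at 8 am on postoperative day 2, and etoricoxib starts that same morning. The committee reviews only after four and 20 participants, and the halt rule needs two stage 3 cases.

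**Conclusion.** The concern holds. The same review is triggered by any doubling in one section and by a persistent, fluid-refractory doubling in another, with no rule of precedence. The consequence is modest: the primary endpoint, sample size and power are unaffected, and few events are expected among 40 participants after exclusion of known risk factors for acute kidney injury. Neither the number of participants affected nor any delay can be computed from the document. The conclusion assumes that the missing figures and the sampling appendix do not settle the point; Figure 2 is cited on the urine output limb, so it may not. The sentence should be corrected because it governs individual safety.

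**What to change.** In Nephrologist review triggers, state the creatinine trigger as any plasma creatinine at least 2 times baseline (at least 100% above) within 30 days, reviewed within 12 hours. Delete the word *persistent* and the clause on adequate fluid resuscitation from that trigger, so that it matches Study design.

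Leave the stage 3 halt rule as it is. It suspends the whole trial, so requiring a confirmed event is reasonable there.

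Aligning Study design to the narrower wording would also remove the conflict, but *persistent* and *adequate* would then need definitions, for example the number and timing of repeat samples. The broader trigger is preferable because it sits better with the Aims, where "Harm is defined in the widest sense of the word in order to detect any degree of harm", though that is a judgement and not something the text compels.

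The cost is one sentence in a protocol amendment and at most a few extra reviews by an on-site nephrologist among 40 participants.

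### The halt trigger counts only a persistent 3-fold creatinine rise with no clear-cut other cause, so early renal replacement or death in the Low arm is not counted, and cause is judged before the committee is called

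*Protocol*

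**What the plan says.** Three adjacent paragraphs of the Step-by-step protocol bear on this.

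- **Study halt triggers.** The order of steps is fixed: "the study will be halted pending urgent review by the independent Monitoring Committee if the following occurs". The event is "Two or more participants in the intervention arm develop AKI Network (AKIN) stage 3 AKI per creatinine criteria", spelled out as "persistent elevations of plasma creatinine $\geq 200\%$ above baseline despite adequate fluid resuscitation". It must also fall "within seven days after surgery and in the absence of a clear-cut alternative cause (such as major systemic complication of surgery").
- **Independent Monitoring Committee.** Two independent nephrologists will "review individual clinical outcomes as well as postoperative changes in plasma creatinine in all participants after completion of four and 20 participants". The halt trigger is additional to these two reviews.
- **Nephrologist review triggers.** The study nephrologist sees, within 12 hours, any participant with no urine response to a 2 L bolus or with stage 2 AKI by creatinine (at least 100% above baseline) "within 30 days, and institute adequate therapy". That review does not halt the study and is not stated to inform the committee.

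Neither renal replacement therapy nor death appears in the halt trigger or in any other halt rule.

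**The concern.** A halt rule should reach the committee at least as surely for the worst outcomes as for a laboratory rise. This one may not, for two reasons.

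First, the event is defined by creatinine alone. Renal replacement lowers plasma creatinine, and death ends its measurement. Either can keep a participant from ever showing a persistent 3-fold rise.

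Second, the absence of a clear-cut alternative cause is part of the trigger itself. A case judged to have such a cause is set aside before the urgent review begins, although the committee exists to give an independent opinion on cases of this kind.

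At stake is continued enrolment to the Low arm without committee review after two serious events. This matters most in the second half of the trial, where no scheduled committee review remains.

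**Working it through.** **1. What the rule counts.** Applying the wording literally to a Low-arm participant within seven days of surgery:

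| Course | Counts as written | Counts after the change |
|---|---|---|
| Persistent rise of at least 200%, no clear-cut other cause | yes | yes |
| The same, followed by renal replacement or death | yes | yes |
| Renal replacement started between 100% and 200%; 200% never reached | no | yes |
| Renal replacement or death after 200% is reached but before it is shown to persist | no | yes |
| Death before 200% is reached | no | yes |
| Persistent rise of at least 200% with a clear-cut other cause | no | yes; committee judges cause |

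Two participants from the four lower rows give a count of zero, and the trial continues.

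**2. When the committee would see them.** The scheduled reviews take place "in all participants after completion of four and 20 participants" and cover individual clinical outcomes, so such cases among the first 20 would be seen at one of these. For participants 21 to 40 (40 − 20 = 20) no review is scheduled, and the halt trigger is the only stated route.

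**3. Arm size.** The protocol gives no operating characteristics for the halt rule, so there is no figure of its own to reproduce for it. The arm size comes from Statistical considerations (margin 15 ng/ml, SD 15 ng/ml, one-sided 0.05, power 90%, 10% dropout):

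n = 2 × (15/15)² × (1.645 + 1.282)² = 17.13, rounded up to 18; 18 / 0.90 = 20 per arm.

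This agrees with the protocol's 18 completing and 20 recruited.

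**4. Illustration of sensitivity.** Let p be the true risk of a severe renal event in the Low arm and c the share of such events that meet the trigger as written. The protocol gives neither; both are assumptions. With q = p × c,

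P(at least 2 of 20) = 1 − (1 − q)²⁰ − 20q(1 − q)¹⁹.

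Worked for p = 10%, c = 1: 1 − 0.1216 − 0.2702 = 0.608.

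| p | c = 1 | c = 0.75 | c = 0.50 | c = 0.25 |
|---|---|---|---|---|
| 5% | 0.264 | 0.172 | 0.088 | 0.026 |
| 10% | 0.608 | 0.449 | 0.264 | 0.088 |
| 20% | 0.931 | 0.824 | 0.608 | 0.264 |

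These are chances of ever reaching two events, including a second event in the last participant, when a halt protects nobody. Reaching two within the first 10 Low-arm participants (half the arm) has probability 0.086, 0.264 and 0.624 at c = 1, and 0.025, 0.086 and 0.264 at c = 0.50, for p = 5%, 10% and 20%.

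**The case against.** The best defence is that the trigger is one layer of several. The nephrologist reviews participants in either arm from stage 2 upward for 30 days. The committee sees all clinical outcomes at two points, and complications to 30 days are recorded and graded. The cause condition is narrow: only a clear-cut alternative removes a case, so doubtful ones still count. Importance cites a 35–55% complication risk in colorectal surgery, so some filter against halts for surgical complications is reasonable. The route through renal replacement is hypothetical, because the protocol never mentions dialysis and does not define the therapy the nephrologist may start. The statement in Aims about detecting any degree of harm concerns the choice of renal measurements and sets no standard for halting. All of this stands and limits the weight of the point. It does not close the gap: the nephrologist review neither halts the study nor is stated to reach the committee, and the scheduled reviews stop at 20.

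A reader might infer more than the text supports:

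- *That unblinded trial staff decide cause.* The protocol does not name who decides or say whether that person knows the allocation. It shows only that the decision precedes the urgent review.
- *That any participant who is dialysed or dies goes uncounted.* One who does so after a persistent 3-fold rise, with no clear-cut other cause, is counted.
- *That counting only Low-arm events is a fault.* This is a common choice for a halt rule, and the change below keeps it.

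**Conclusion.** The point holds in a limited form. Followed exactly, the halt rule could let two Low-arm participants start renal replacement or die early without a halt. It could also set aside a stage 3 case on grounds of cause before the committee's urgent review. For the second half of the trial nothing else in the protocol is stated to bring such cases to the committee.

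The loss of sensitivity cannot be quantified from the protocol. The tabulated probabilities are arithmetically right, but the event risks and the share lost are assumed, and patients with known AKI risk factors are excluded. A share lost of one half simply halves the risk in the formula. Much of the low sensitivity comes from requiring two events among 20 people, not from the event definition: at an assumed 10% risk, even complete counting gives only 61%. The figures should not be read as an estimate of the defect.

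This is an inexpensive improvement to trial conduct. It does not affect the primary NGAL comparison.

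**What to change.** Under Study halt triggers:

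1. Define a halt event as stage 3 AKI by creatinine as now described, or start of renal replacement therapy, or death, within seven days after surgery in the intervention arm.
2. Remove the alternative-cause condition from the trigger and state that the Monitoring Committee judges cause in its urgent review.
3. Keep the count of two and the seven-day window.

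This changes two phrases, needs no new body and leaves the sample size as it is. The price is that an event unrelated to the intervention may contribute to a brief pause while the committee reviews it. The change does not add a committee review after participant 20 and does not raise sensitivity beyond what a two-event rule in 20 participants allows (the c = 1 column).

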30-day incidence of complications (including AKI) classified and defined as per Auckland ERAS database, graded per Clavien-Dindo grading scale
Length of stay, time to repeated flatus
IV and oral fluid volumes and changes in body weight and lean tissue mass (BIA)

Depending on the findings of the independent Monitoring Committee, the study may then close or resume with changes as recommended.

Endpoints

The primary endpoint is urinary concentration of NGAL at 2 pm on POD 1. Secondary endpoints are listed in Table 3.

Urine samples are collected once at the preoperative research visit and at regular intervals during and 72 hours after surgery and once on POD 30 (See further Blood and urine sampling protocol).

Plasma samples are collected three times at the preoperative research visit, at regular intervals during and 72 hours after surgery and once on POD 30. In addition, two more samples are taken when the sinistrin-PAH test is repeated 0800-1100 on POD 1 (See further Blood and urine sampling protocol).

Clinical data including demographics, diagnosis, surgery, anaesthesia, complications and recovery parameters are prospectively collected as per standard practice by an ERAS Nurse Specialist in the Auckland ERAS database.

Sample handling and analysis

A research fellow or a research nurse will collect all samples. Some assays will be performed on collection by Waitemata DHB Laboratories; others will be stored in a dedicated -80°C alarmed research freezer at Waitemata DHB Laboratories for later batch analyses by the Christchurch co-investigators. All assays will be performed by staff unaware of participants' group allocation.

Statistical considerations

On the basis of a recent study in surgical trauma, the mean (SD) urinary NGAL concentration at 2pm on the first postoperative day in the control (High) group is assumed to be 10 (10) ng/ml, and the clinically significant cut-off in the Low group is assumed to be 25 ng/ml. To show non-inferiority with 90% power, a minimum of 18 participants completing the study per treatment group will be needed based on a margin of non-inferiority of 15 µg/L (25-10 ng/ml), a common SD of 15 ng/ml, and 0.05 one-sided significance level. Assuming 10% dropout, 20 participants per treatment group will be recruited (40 participants in total).

Certain data indicate that urinary NGAL follows a log-normal distribution. To ensure this will not increase the sample size required, a sample size calculation taking this into account

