has also been performed. This indicates that a minimum of 31 participants, 15.3 in each treatment arm, will be needed based on a margin of non-inferiority of log 15 ng/ml and an SD of log 10 ng/ml, with 90% power using a one-sided statistical test with an alpha level of 0.05. A sample size of 40 patients will therefore be sufficient should urinary NGAL be log-normally distributed in the planned study. This sample size calculation was performed with the assistance of [name], Waitemata DHB statistician.

Repeated measures will be analysed by analyses of variance for repeated measures (time x treatment group with post-hoc Tukey's test as appropriate) or mixed regression models if appropriate. Student's unpaired t-test or, if non-normally distributed, Mann-Whitney U test and Fisher's exact test will be used as appropriate.

Planned subgroup analysis are: moderate vs no chronic kidney disease, patients with vs without epidural analgesia, patients undergoing surgery via laparotomy vs laparoscopy.

Appendices

1. Blood and urine sampling protocol
2. Clearance studies protocol

References

Sweny P. Is postoperative oliguria avoidable? *Br J Anaesth*. 1991;67:137-145.

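### The log-normal sample-size check uses a margin and an SD that are not log-scale quantities, so the adequacy of 40 patients under log-normality depends on the SD and is not shown

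*Protocol*

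**What the plan says.** All of this is in the protocol, Statistical considerations.

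- **Assumptions.** Urinary NGAL at 2 pm on POD 1 "in the control (High) group is assumed to be 10 (10) ng/ml". For the other arm, the protocol adds that "the clinically significant cut-off in the Low group is assumed to be 25 ng/ml".
- **Main calculation (raw scale).** The margin is 15 ng/ml, the difference between 25 and 10, with "a common SD of 15 ng/ml, and 0.05 one-sided significance level" and 90% power. This gives 18 completers per arm, or 20 per arm recruited after 10% dropout.
- **Log-normal check.** Because some data suggest that NGAL is log-normal, a second calculation is made "based on a margin of non-inferiority of log 15 ng/ml and an SD of log 10 ng/ml". The test is said to be one-sided at 0.05, and the power 90%. Its result: "This indicates that a minimum of 31 participants, 15.3 in each treatment arm, will be needed".
- **Conclusion drawn.** "A sample size of 40 patients will therefore be sufficient should urinary NGAL be log-normally distributed in the planned study".

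**The concern.** A margin on the log scale is a difference of logs, that is, the log of a ratio. Taking the log of a difference in ng/ml gives something else: read as a log-scale margin, log 15 is a 15-fold ratio (150 against 10 ng/ml), whereas the stated cut-off of 25 against 10 is a 2.5-fold ratio. Likewise, the SD of log NGAL is not the log of the SD of NGAL. Read literally, a log SD of ln 10 = 2.30 corresponds to a CV of about 14, against a CV of 1.0 for 10 (10).

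Two further points need explaining. The reported 15.3 per arm does not follow from the reported inputs. And the check is built on an SD of 10, whereas the main calculation uses 15, with no reason given for the change.

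This paragraph is the protocol's only justification for saying that log-normality does not raise the sample size. If it fails, the trial could have less than its planned 90% power for a skewed primary endpoint, and the protocol would not say so.

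**Working it through.** **Method.** Non-inferiority of two means, 1:1 allocation, no true difference: n per arm = 2 (z_α + z_β)² SD² / margin². For one-sided 0.05 and 90% power, 2 × (1.645 + 1.282)² = 17.13. For two-sided 0.05, 2 × (1.960 + 1.282)² = 21.01. Sample sizes marked t, and all powers, use the noncentral t distribution.

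**1. Main calculation.** SD 15, margin 15: 17.13 × (15/15)² = 17.1 by z, 17.8 by t, so 18 per arm (power 0.902), and 18/0.9 = 20. It reproduces.

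**2. Log-normal check with its printed inputs.** The ratio log 15/log 10 = 1.176 is the same in any log base.
- One-sided 0.05, as stated: 17.13/1.176² = 12.4 by z; 13.1 by t, so 14 per arm. The protocol prints 15.3.
- Two-sided 0.05: 21.01/1.176² = 15.2 by z, 30.4 in total, which rounds up to 31. Rounding the ratio to 1.17 gives 15.35.

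The printed figure is therefore close to a two-sided normal-approximation result, although the text says one-sided.

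**3. Log-scale inputs implied by the protocol's own figures.** Assumptions: 10 and 25 ng/ml are arithmetic means, and the CV is equal in both arms, so that the ratio of means equals the ratio of geometric means.
- Margin: ln(25/10) = 0.916.
- Log SD = √ln(1 + CV²). Mean 10, SD 10: CV 1.0, √ln 2 = 0.833. Mean 10, SD 15: CV 1.5, √ln 3.25 = 1.086.

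**4. Corrected check, one-sided 0.05, 90% power.**

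| | CV 1.0 (SD 10 at mean 10) | CV 1.5 (SD 15 at mean 10) |
|---|---|---|
| Log SD | 0.833 | 1.086 |
| n per arm, z | 17.13 × (0.833/0.916)² = 14.1 | 17.13 × (1.086/0.916)² = 24.0 |
| n per arm, t | 14.9, so 15 | 24.8, so 25 |
| Power at 18 per arm | 94% | 80% |
| Power at 20 per arm | 96% | 84% |

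**5. Break-even.** With 18 completers per arm, 90% power holds up to a log SD of about 0.92, a CV of about 1.15. The two SDs in the protocol, taken at a mean of 10, fall on either side of it.

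**The case against.** The strongest reply is that the conclusion survives. The only mean and SD that the protocol gives as a pair is 10 (10). A proper log-scale calculation from that pair needs 15 per arm, 30 in total, almost the printed 31. N itself comes from the raw-scale calculation, which reproduces. This stands, and it means that the claim about 40 patients is not shown to be false.

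The 80% figure also needs an added step: pairing the common SD of 15 with a mean of 10. The protocol never states a CV of 1.5, and the 15 may be a cautious raw-scale allowance. If it belonged to a mean of 25, the CV would be 0.6 and the requirement 8 per arm by t; at a mean of 17.5, 12 per arm. So 80% is the unfavourable end of a range. This too stands. What remains is that the protocol does not say which reading applies, and the answer turns on it.

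The mismatch in 15.3 is conservative, because the printed inputs need fewer patients than reported. It does not by itself threaten N. Its origin is not certain either: dividing the one-sided t result by the worst-case Mann-Whitney efficiency, 13.1/0.864, also gives 15.2, although the text mentions no such inflation.

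A reader might infer two stronger things. One is that the trial would accept a 15-fold rise as non-inferior. The documents do not support this: log 15 appears only in the sample-size check, and the margin and cut-off tied to the trial are 15 and 25 ng/ml. The other is that the trial is underpowered outright. That holds only under the CV 1.5 reading.

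**Conclusion.** The log-normal check is wrong as written. Its margin and SD are not log-scale quantities, they conflict with the protocol's own 10 (10) and 25 ng/ml, and its result does not follow from them at the stated one-sided 0.05. The stated sidedness may be wrong.

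Whether 40 patients suffice under log-normality is conditional: yes at CV 1.0; short of 90% power at CV 1.5, where 25 completers per arm would be needed against 18 planned. The printed calculation does not settle which applies. These figures also assume no true difference between arms. The main raw-scale calculation is unaffected.

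**What to change.** Replace the log-normal paragraph. State:

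- the margin as a geometric mean ratio of 2.5 (25/10), log-scale 0.916;
- a log SD derived from a stated CV, with a sentence reconciling it with the common SD of 15 in the main calculation;
- the alpha and sidedness actually used;
- the resulting power with 18 completers per arm at one-sided 0.05: 94% at CV 1.0 and 80% at CV 1.5.

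Delete log 15, log 10, 15.3 and 31. Keep N = 40, and replace the unconditional sufficiency sentence with one that names the CV on which it depends.

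The cost is a rewritten paragraph and, under the less favourable SD, an openly stated power below 90%. No extra patients are required, and the endpoint and the 15 and 25 ng/ml figures do not change.
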